**Second Malignancy:**

A second malignancy is one unrelated to the treatment of a prior malignancy (and is NOT a metastasis from the initial malignancy). Second malignancies require ONLY routine reporting unless otherwise specified.

Whenever possible, the CTEP-AERS reports for new malignancies should include tumor pathology, history or prior tumors, prior treatment/current treatment including duration, any associated risk factors or evidence regarding how long the new malignancy may have been present, when and how it was detected, molecular characterization or cytogenetics of the original tumor (if available) and of any new tumor, and new malignancy treatment and outcome, if available.

- Pregnancy loss
  - Pregnancy loss is defined in CTCAE as “Death in utero.”
  - Any Pregnancy loss should be reported expeditiously, as Grade 4 “Pregnancy loss” under the Pregnancy, puerperium and perinatal conditions SOC.
  - A Pregnancy loss should NOT be reported as a Grade 5 event under the Pregnancy, puerperium and perinatal conditions SOC, as currently CTEPAERS recognizes this event as a patient death.
  - A neonatal death should be reported expeditiously as Grade 4, “Death neonatal” under the General disorders and administration SOC.
  - The reporting of adverse events described above is in addition to, and does not supplant, the reporting of adverse events as part of the reporting of the results of the clinical trial, e.g. routine reporting.

## 10.5 Other Required Expedited Reporting

EVENT TYPE	REPORTING PROCEDURE
Other Grade 4 or 5 Events and/or Any Hospitalizations During Treatment Not Otherwise Warranting an Expedited Report	Complete a Notification Form: Grade 4 or 5 Non-AER Reportable Events/Hospitalization Form electronically via the NCCTG Remote Data Entry System within 5 working days of the date the clinical research associate (CRA) is aware of the event(s) necessitating the form. If an CTEP-AERS report has been submitted, this form does not need to be submitted.

## 10.6 Adverse events to be graded at each evaluation.

Pretreatment symptoms/conditions are to be evaluated at baseline per CTCAE v4.0 grading unless otherwise stated in the table below:

System Organ Class (SOC)	Adverse event	Baseline	Each evaluation
Nervous System Disorder	Headache	X	X

Refer to the instructions in the Forms Packet (or electronic data entry screens, as applicable) regarding the submission of late occurring AEs following completion of the Active Monitoring Phase.

## 11.0 TREATMENT EVALUATION

### 11.1 Patient Self-Report Measures

The Patient self-report measures will be given three times, baseline and after weeks 4 and 8 of treatment. These items together take approximately 20 - 25 minutes to complete.

Fatigue is measured by multiple approaches in this protocol to not only provide a complete description of the type of fatigue experienced throughout treatment by the patients but also to inform future studies as to the relative merit (reliability, validity, responsiveness) the alternative methods impart in measuring fatigue.

#### 11.1.1 Brief Fatigue Inventory (BFI)

The BFI is a 9-item instrument that allows for the rapid assessment of fatigue level in cancer patients and identifies those patients with severe fatigue. Three items ask patients to rate their fatigue for “now,” and fatigue at its “worst” and “usual” for the last 24 hours. The 11-point scales are bounded by 0 = “no fatigue” and 10 = “fatigue as bad as you can imagine.” Using the same type of scales, the remaining questions ask patients to rate how their fatigue interferes with several quality of life domains including general activity, walking, mood, work, and relations with others. These scales are bounded by 0 = “does not interfere” and 10 = “interferes completely.” The reliability and validity of the BFI were demonstrated in a study of 305 cancer patients and 290 community-dwelling adults. An internal consistency coefficient (Cronbach’s alpha) = 0.96 was demonstrated when the BFI was administered to 305 patients with cancer (80). The BFI has been demonstrated as viable primary endpoints for numerous cancer clinical trials and has been translated into 22 different languages (81).

Single-question assessment is the most commonly used and the most useful methodology. A score of 1–3 indicates the presence of mild fatigue that does not require clinical intervention, and scores of 4–6 and 7–10 indicate moderate and severe fatigue, respectively, which require further evaluation and clinical intervention (82).

### 11.1.2 PROMIS

The PROMIS fatigue short form is a 7-item assessment using 5 response categories similar to the initial FACT series of measures. It produces a single summated score for fatigue (91). It was recently endorsed by the NCI SxQOL Steering Committee for use in NCI-sponsored cancer control trials. It produces a single summative score for the purposes of analysis.

The PROMIS measure will be used mostly as an exploratory secondary measure. We will look at its psychometric properties with the population in this study and also look at concurrent validity using the BFI as a gold standard. There are two domains represented by the 7 items in the PROMIS fatigue short form; impact and experience. In an exploratory manner, these will be evaluated as subscales but also the scale will be evaluated as a unidimensional measure. Since the fatigue items have not been, to our knowledge, psychometrically validated in cancer populations, we do see the use of PROMIS fatigue as an exploration. Since there is a desire to use a core set of measures in fatigue studies going forward and PROMIS has been cited as being a logical set of measures to use in this regard, we felt it was important to include these and begin generating some psychometric data, particularly in this, more rare population of high grade glioma patients.

### 11.1.3 PRO-CTCAE

PRO-CTCAE Symptomatic adverse events (AE) in cancer trials are reported by clinicians using the National Cancer Institute's (NCI) Common Terminology Criteria for Adverse Events (CTCAE). To integrate the patient perspective into AE reporting, NCI contracted (HHSN261201000043C) to create a patient-reported outcomes companion tool (PRO-CTCAE). The validity and reliability of PRO-CTCAE's 124 items reflecting 78 symptomatic AEs is presently underway. The items being created and validated are intended to be complementary to existing symptom items in the NCI's Common Terminology Criteria for Adverse Events (CTCAE). The CTCAE is an existing lexicon of clinician-reported adverse event items required for use in all NCI-sponsored trials. The goal of developing patient versions of CTCAE symptom items is to improve the accuracy and precision of adverse symptom assessment in cancer trials, and to bring the CTCAE into harmony with other areas of clinical research in which the gold standard for symptom evaluation is patient self-reporting. Information gathered through the PRO-CTCAE is intended to provide clinicians with more comprehensive information about the patient experience with treatment when trials are completed and reported. We are including six items from the PRO-CTCAE in this study for fatigue and cognitive function to provide further evidence of their reliability and validity and compare the PRO-CTCAE items to the other methods for assessing fatigue and cognitive function.

### 11.1.4 LASA

Linear Analogue Self-Assessment (LASA) items have been validated as general measures of global QOL dimensional constructs in numerous settings (83-88). A series of five LASA items have been constructed and validated at Mayo for use in cancer patients (89). The 5 aspects measured will be global QOL, physical, emotional, spiritual, and intellectual well-being. [name] and colleagues have done extensive research on the application of single-item LASA measures for assessing a wide variety of PROs including fatigue, peripheral neuropathy, hot flash activity, and anxiety. These single-item assessments have become the most-used assessment in all NCI-sponsored cancer control studies (90). As a result of recent research, this study includes LASA measures for global QOL and fatigue and will include these measures in all future phase II and phase III clinical trials as an independent prognostic factor independent of performance status.

### **11.1.5 FACT-Cog (Secondary Cognitive Endpoint)**

Patients in this study will self-report their perceived cognitive functioning using the FACT-Cog version 3 (92). For many cancer-related symptoms, given their subjective nature, self-report is the only way an assessment can be conducted. The FACT-Cog is a useful measure of perceived cognitive deficits and related quality of life for adults undergoing chemotherapy, and is the first patient-reported outcomes measure to be developed and validated with a sample of cancer patients. The scale measures the frequency of positive and negative cognitive functioning events over the past seven days, based on self-report. The measure utilizes a five-point Likert-type scale (ranging from 0 = never to 4 = several times a day) to assess several different aspects of cognitive function. Lower scores are indicative of poorer perception of functioning. The FACT-Cog assesses a broad range of cognitive domains (not just those specifically related to work) and provides a multidimensional view of the cognitive deficits often experienced by patients with cancer.

### **11.1.6 Godin Leisure Time Exercise Questionnaire (GLTEQ).**

The amount of leisure time spent in physical activity will be assessed using the Godin Leisure Time Exercise Questionnaire (GLTEQ) (103). The GLTEQ consists of two questions designed to assess the frequency within a typical 7 day week of mild, moderate, and strenuous exercise performed for a duration of at least 15 minutes during a participant's free time. The measure is easily administered and brief, with a retest coefficient of .62, a concurrent coefficient of .32 and an objective validity coefficient of .56 compared with CALTRAC accelerometry, estimated VO2 max and body composition (via hydrostatic weight).18 The GLTEQ has also been used successfully in populations of adult cancer patients (104-108).

## **11.2 Objective Cognitive Measures (Primary Cognitive Endpoint)**

The neuropsychological battery proposed for this study overlaps with batteries used in numerous North Central Cancer Treatment Group (NCCTG) multi-center trials for studies in patients with CNS tumors without any problems or complications.

Clinicians and researchers must balance the often conflicting goals of obtaining valid PRO data while not burdening patients or interfering with the provision of care in a busy clinical setting. When surveyed about the preferred properties for an assessment battery for neurological and behavioral function, 191 experts in clinical and epidemiologic research reported it should be brief, precise, and easy to administer, score, and interpret (93).

The Symbol Digit Modalities Test (SDMT; Smith, 1982) is a measure of attention, visual tracking, and psychomotor speed. The task consists of a brief practice, followed by a 90-second test trial. Subjects are given a key in which 9 symbols are paired with each of the digits 1 through 9. Below the key is a grid in which a random series of the symbols appear above empty boxes. The task is to fill in the correct digit under each symbol, without skipping boxes, as quickly as possible for 90 seconds. This task has been found to be a particularly sensitive indicator of brain dysfunction (95).

### **11.2.1 Controlled Oral Word Association**

This test requires subjects to generate words beginning with specified letters. A brief practice is followed by three 60-second trials using three different first-letter cues. This is a measure of processing speed and phonemic verbal fluency, and is a task widely used in neuropsychological assessment.

### **11.2.2 Trail Making Test**

Trail Making is a two-part sequencing task which requires subjects to connect numbered dots in order (Part A) and then to connect dots alternating between numbers and letters (Part B). Score is time of completion, with each trial scored separately. Part A measures psychomotor speed, concentration, and visual scanning. Part B requires the cognitive functions required for Part A, with added recruitment of cognitive flexibility (executive function) (86). This test has a long history of use in clinical neuropsychology, and has been found to be very sensitive to brain dysfunction in general (96, 97).

## 12.0 DESCRIPTIVE FACTORS

None.

## 13.0 TREATMENT/FOLLOW-UP DECISION AT EVALUATION OF PATIENT

If the patient discontinues the study agent prior to 8 weeks, the patient will go off study.

A patient is deemed *ineligible* if after registration, it is determined that at the time of registration, the patient did not satisfy each and every eligibility criteria for study entry. If the patient received treatment, all data up until the point of confirmation of ineligibility must be submitted. If the patient never received treatment, on-study material must be submitted.

A patient is deemed a *major violation*, if protocol requirements regarding treatment in cycle 1 of the initial therapy are severely violated that evaluability for primary end point is questionable. All data up until the point of confirmation of a major violation must be submitted.

A patient is deemed a *cancel* if he/she is removed from the study for any reason before any study treatment is given. On-study material and the End of Active Treatment/Cancel Notification Form must be submitted. No further data submission is necessary.

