## **8.0 DOSAGE MODIFICATION BASED ON ADVERSE EVENTS**

The study medication dose should be stopped for any grade 3 or worse toxicities related to study agent, or at the patient's discretion regarding toxicity. Any of the above should be clearly recorded on the Adverse Event Form.

Patients can be discontinued abruptly (no need to taper).

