## **9.0 ANCILLARY TREATMENT/SUPPORTIVE CARE**

Patients who begin using any other pharmacologic agents or nonpharmacologic interventions after registration to specifically treat fatigue including psychostimulants, antidepressants, acupuncture, etc. will be taken off study.

**Note:** Antidepressants used to treat items other than fatigue (such as hot flashes or depression) are allowed if the patient has been on a stable dose for  $\geq$  28 days and plans to continue for the duration of the trial. Erythropoietin agents to treat anemia are allowed.

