### 16.3 Primary Endpoint

The primary endpoint of this trial is the response rate in terms of a clinically meaningful improvement in patient-reported fatigue at 8 weeks. A response is defined as an improvement of 2 points on the 0-10 scale of the usual fatigue on the BFI.

All patients meeting the eligibility criteria who have signed a consent form, have begun treatment, and have not had a major treatment violation within the 1st cycle of treatment will be evaluable for the primary endpoint. Patients will be analyzed according to the arm in which they were randomized.

Comparison of the primary endpoint between arms will be based on a binomial point estimate computed for each arm and a Fisher's exact test will be the inferential hypothesis test.

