## 16.5 Statistical Design

The primary endpoint for the trial is the response rate in terms of a clinically meaningful improvement in patient-reported fatigue, defined as at least a two-point improvement in fatigue as measured by the usual fatigue item from the Brief Fatigue Inventory at 8 weeks. This change

will be from baseline to 8 weeks (after randomization). The design proposed for this study will randomize a maximum of 330 evaluable patients to one of three treatment arms.

**Efficacy stopping rules:** This study will be monitored by Alliance Data and Safety Monitoring Board (DSMB) every 6 months for safety and efficacy. If at any time prior to full accrual the p-value for the Fisher's exact test that an arm is superior to the other arm given all available data falls below 0.001 then consideration will be given to stopping the trial early.

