#### **FOLLOW UP:**

Phone call schedule: Call patient at home the end of study weeks 4 and 8. This is to remind patient to take the study agent as instructed, document compliance, encourage completion of the booklet, and address problems. If the patient is seen in clinic, this phone call can be omitted.

•  
3. Items to document:

- Date of phone call
- Study week
- Questions/Comments
- Performance Status Score
- AE assessment end of weeks 4 and 8

If the patient reports any side effects, please document:

- o Side effects:
  - Headache
  - Any others - Severity and attribution, if applicable.

4. Reinforce compliance with study medication.

5. Reinforce completion of questionnaires and request return of them at end of the month.

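### Patients who stop study drug or start another fatigue treatment go off study, and nothing asks for their week-8 BFI although they stay evaluable for the primary endpoint

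*Combined protocol and SAP*

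**What the plan says.** - **Leaving the study.** Section 13.0: "If the patient discontinues the study agent prior to 8 weeks, the patient will go off study". Section 9.0: patients who begin other agents or interventions "to specifically treat fatigue including psychostimulants, antidepressants, acupuncture, etc. will be taken off study". Section 8.0 itself directs some of this stopping: "The study medication dose should be stopped for any grade 3 or worse toxicities related to study agent". It also allows stopping for toxicity at the patient's discretion.
- **Assessment.** Under Section 11.1 the self-report measures are "given three times, baseline and after weeks 4 and 8 of treatment". The test schedule (4.0) and submission timetable (18.2) list the same time points. The phone guide in Appendix XII says: "Call patient at home the end of study weeks 4 and 8". Section 18.2 has a compliance form for a booklet that holds no patient data.
- **Who counts.** Section 16.3 takes eligible, consented patients who began treatment; those with no major violation in the first "cycle of treatment will be evaluable for the primary endpoint". Section 13.0 reserves major violation for cases where "protocol requirements regarding treatment in cycle 1 of the initial therapy are severely violated that evaluability for primary end point is questionable".
- **Data after leaving.** Section 13.0 gives submission rules for ineligible, major-violation and cancelled patients. It gives none for a treated patient who stops early.
- **Missing values.** Section 16.8 lists complete case and four single imputations, for sensitivity, and names none as primary. Section 16.2 adds 30 patients for cancellations, ineligibility and major treatment violations.

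**The concern.** The primary endpoint needs a BFI usual-fatigue score at week 8. Patients who stop for toxicity as the protocol directs, or who seek other help for fatigue, leave the study before that score is due, and no sentence tells a site to obtain it. They remain in the evaluable set all the same. The major-violation category does not absorb them: stopping as directed is not a violation, and the category covers only cycle 1, so it cannot apply to weeks 5 to 8.

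Two things are at stake. Primary-endpoint data may be lost that a mailed booklet could have supplied. And the response rate then depends on a counting rule that the primary analysis does not state. Stopping may also differ by arm: Section 15.1.7 reports that psychiatric symptoms led to discontinuation more often on armodafinil than on placebo. Those were narcolepsy, sleep apnea and shift-work trials, so the size in glioma is unknown.

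**Working it through.** **1. Inputs.** From Section 16.2: placebo response 10%, armodafinil 25%, 100 per arm, two-sided 5% per comparison, Fisher's exact test. All missing fractions below are assumptions, because the documents give none.

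**2. The plan's own figure.** The pooled normal formula is n = [1.960·√(2·0.175·0.825) + 0.842·√(0.10·0.90 + 0.25·0.75)]² / 0.15² = 99.5, so 100 per arm; power by this approximation is 80.2%. The stated n reproduces. Exact power of the named Fisher test sums the binomial probabilities of all outcome pairs with p ≤ 0.05. It is 76.2% at 100 per arm and 80.4% at 110. The comparisons below start from the exact figure.

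**3. Equal loss, unrelated to response.** Complete case keeps the rates and shrinks n to 100(1−m). Non-response keeps n = 100 and shrinks the rates to 0.10(1−m) and 0.25(1−m).

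| Missing in each arm | Complete case | Missing = non-response |
|---|---|---|
| 0% | 76% | 76% |
| 10% | 71% | 70% |
| 20% | 65% | 64% |
| 30% | 58% | 56% |

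The two rules differ by at most about 3 points, so most of the fall is lost data. If all 30 extra patients proved evaluable (110 per arm), complete-case power would go from 80% to 76, 70 and 63%.

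**4. Unequal loss, unrelated to response.** Placebo is 10% missing throughout.

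| Active arm missing | Complete case | Missing = non-response | Rates shown under non-response |
|---|---|---|---|
| 15% | 71.5% | 62.5% | 9% vs 21.25% |
| 20% | 71.0% | 53.9% | 9% vs 20% |
| 30% | 67.2% | 35.8% | 9% vs 17.5% |

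**5. Unequal loss, dropouts truly non-responders.** At 10% placebo and 15% active missing, complete case shows 0.10/0.90 = 11.1% and 0.25/0.85 = 29.4%. The gap is 18.3 points instead of 15. Complete case is significant and non-response is not in about 8% of trials; the figure is about 12% at 10%/20% and 0.5% at 10%/10%. With a true 10% in both arms, complete case compares 11.1% (n = 90) with 11.8% (n = 85) and rejects in about 4% of trials, so the null error rate is not inflated at these rates. One possible data set: 9/90 vs 19/85 gives p = 0.038, and the same responders as 9/100 vs 19/100 give p = 0.065.

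**6. Zero value carried forward.** Section 16.8 does not define it. Section 11.1.1 anchors a BFI score of 0 at no fatigue. If zero meant that score, any dropout with baseline usual fatigue of 2 or more would improve by at least 2 points and count as a responder.

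**The case against.** The collection gap is an inference. Nothing forbids a booklet after a patient goes off study. The words about treatment in Section 11.1 may only mark timing: Section 4.0 times the visits from study drug administration, Section 16.5 counts 8 weeks from randomization, and Appendix XII speaks of study weeks and does not limit its calls to patients on drug. The compliance form in Section 18.2 shows that empty booklets are tracked, and instructions may sit in forms or consent pages that cannot be seen here. All of this stands, and a reader who infers that the plan bars later collection goes too far. But recording that a booklet is empty does not ask for one, and sites could fairly read off study as the end of collection.

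A reader might also infer that the counting rule is wholly open and can be picked after the data are seen. That is too strong. Sections 16.3 and 16.5 define response as an improvement among evaluable patients, so counting a patient without one as a non-responder is a natural reading, and Section 16.8 lists the alternatives in advance. What is missing is the sentence that says so.

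Finally, one might take non-response coding as a nearly free remedy. Step 4 shows otherwise: it is close to complete case only when loss is equal by arm. The example in step 5 falls on both sides of 0.05 by construction and shows what is possible, not what is likely.

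**Conclusion.** The concern holds as a gap in collection. Followed as written, the plan can lose the week-8 BFI of patients whom it still counts as evaluable, and the 30 extra patients are not allotted to that loss. On the assumed equal losses of 10, 20 and 30%, complete-case power falls from 76% to 71, 65 and 58%. The true size is unknown, as is the fraction that collection would recover in high-grade glioma.

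The unstated counting rule is a secondary matter of clarification. Neither complete case nor non-response is safe in every setting: non-response costs much power when loss is unequal and unrelated to response, and complete case overstates the gap when dropouts are non-responders. The documents do not show which mechanism would apply. This should be fixed, with medium confidence; it does not invalidate the design.

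**What to change.** **Main change.** In Sections 13.0 and 9.0, state that these events end protocol treatment but that the scheduled week-4 and week-8 booklets are still collected. Leave the rules on when treatment stops untouched. Section 18.1 already allows return by mail. Cost: a short amendment, a few more booklets and possibly a change of consent wording, which cannot be checked here.

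**Secondary changes.**
- In Sections 16.3 and 16.5, name one primary rule for a week-8 BFI that is still missing, and keep the Section 16.8 methods as sensitivity analyses. If the rule is non-response, state its cost under unequal missingness, as in step 4.
- State how a week-8 score obtained after another fatigue treatment is counted in the primary analysis.
- In Section 16.8, state that zero value does not mean a BFI score of 0.
- Multiple imputation, which Section 16.8 does not list, could be added but is optional.

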**15.1.7 Known potential toxicities**

The use of armodafinil is contraindicated in patients with hypersensitivity to armodafinil, modafinil, or any component of the formulation.

Use is not recommended in patients with a history of angina, cardiac ischemia, recent history of MI, left ventricular hypertrophy, or patients with mitral valve prolapse, who have developed mitral valve prolapse syndrome with previous CNS stimulant use.

Angioedema and hypersensitivity (with rash, dysphagia, and bronchospasm) have been observed with armodafinil. Small average increases in mean systolic and diastolic blood pressure were seen in patients with narcolepsy taking armodafinil when compared to placebo.

Serious and life-threatening rashes including Stevens-Johnson syndrome, toxic epidermal necrolysis, and drug rash with eosinophilia and systemic symptoms have been reported with modafinil, the racemate of armodafinil. Most cases have been reported within the first 5 weeks of therapy.

In pre-approval narcolepsy, OSA and SWD controlled trials of armodafinil, anxiety, agitation, nervousness, irritability, and depression were reasons for treatment

discontinuation more often than for placebo. Cases of suicide ideation were also observed in clinical trials.

The use of armodafinil may impair the ability to engage in potentially hazardous activities.

The agent should be administered at a reduced dose for patients with severe hepatic impairment. There is inadequate information to determine the safety and efficacy of dosing patients with severe renal impairment. Elimination of the agent and its metabolites may be reduced in elderly patients. Consideration should be given to the use of lower doses in this population.

Headaches are dose related and reported in > 10% of patients. Adverse reactions reported in 4 to 10% of patients include nausea (dose related), dizziness, insomnia (dose related), anxiety, and diarrhea. Adverse events reported in < 4% of patients include: depression (dose related), dyspepsia, fatigue, palpitations, rash (dose related), upper abdominal pain, agitation, anorexia, constipation, contact dermatitis, decreased appetite, depressed mood, attention disturbance, dyspnea hyperhidrosis, increased heart rate, flu-like syndrome, loose stools, migraine, nervousness, pain, paresthesia, polyuria, pyrexia, thirst, tremor, xerostomia (dose related), and vomiting.

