### 16.2 Sample Size

On average, we recruit six patients per month for GBM treatment trials. For symptom control studies with heterogeneous populations, such as N05C7 (Concerta), we were able to average 25 patients a month. We have found that symptom management trials targeting symptoms with a high prevalence have rapid accrual. Therefore, for this study, a reasonable conservative estimate for this more homogeneous population would be 8 patients a month. With 330 patients, accrual would be completed in 41 months.

The randomized design to be utilized is described below. Based on our previous work, we estimate that the response rate for the placebo arm will be 10%. We design the study with 100 patients per arm so that the Fisher’s exact test will have 80% power to detect a response rate of 25% with a two-tailed alternative and a 5% Type I error rate for each treatment comparison to the placebo. Again, we are not using a conservative multiple contrasts approach because we want to err on the side of accepting a modest armodafinil effect. We plan to accrue an additional 30 patients to account for patient cancellations, ineligibility, or major treatment violations. Therefore, there will be a maximum of 330 patients accrued to this study unless undue adverse events are encountered.

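### The primary analysis drops patients with a loosely defined cycle 1 treatment violation, and no all-treated analysis is planned, so the dose-versus-placebo comparisons can be biased

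*Combined protocol and SAP*

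**What the plan says.** Section 16.3 makes a patient evaluable for the primary endpoint if he or she is eligible, consented, and meets two further conditions: to "have begun treatment, and have not had a major treatment violation within the" first cycle. The schema sets cycle 1 at four weeks. The section adds: "Patients will be analyzed according to the arm in which they were randomized".

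Section 13.0 gives a patient the violation label when "protocol requirements regarding treatment in cycle 1 of the initial therapy are severely violated that evaluability for primary end point is questionable". It gives no dose count or adherence threshold and names no adjudicator. The same section states: "If the patient discontinues the study agent prior to 8 weeks, the patient will go off study".

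Section 16.2 says: "We plan to accrue an additional 30 patients to account for patient cancellations, ineligibility, or major treatment violations". Violators are therefore replaced by extra accrual and not analysed.

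Section 8.0 says: "The study medication dose should be stopped for any grade 3 or worse toxicities related to study agent". It also lets the patient stop at his or her own discretion over toxicity.

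Section 15.1.7 says: "Headaches are dose related and reported in > 10% of patients". It marks nausea and insomnia, among others, as dose related too.

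Section 16.8 lists complete-case analysis and several single imputations without naming a primary method. It deals with missing values and does not say that excluded patients are put back.

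**The concern.** The trial asks whether a patient assigned to 150 mg or 250 mg responds more often than one assigned to placebo. Randomisation protects that comparison only while the analysed groups are the randomised groups. How treatment went in weeks 1 to 4 is an outcome of treatment. If tolerability affects dosing, and tolerability depends on dose, the excluded patients can differ between arms in number and in prognosis. Analysis by assigned arm does not repair this, because it applies only to patients still in the set.

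The consequence is practical. Section 16.1 uses these comparisons to choose a dose for phase III, with no multiplicity adjustment. If a removed patient would have counted as a non-responder, the arm that loses more such patients shows a higher response rate than was achieved among those assigned to it.

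**Working it through.** **Inputs.** From 16.2: placebo response 10%, target 25%, 100 evaluable per arm, two-sided 5% Fisher's exact test for each dose against placebo, 330 accrued, 30 of them allowed for losses. With three equal arms, 330/3 = 110 randomised per arm. The number and arm split of major violations are not in the documents, so a range is assumed.

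**The plan's own figure.** The pooled normal approximation is

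n = [1.96·√(2·p̄·(1−p̄)) + 0.8416·√(p1(1−p1) + p2(1−p2))]² / (p2−p1)²

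With p1 = 0.10, p2 = 0.25 and p̄ = 0.175 this is (1.96·√0.28875 + 0.8416·√0.2775)² / 0.0225 = (1.0532 + 0.4434)² / 0.0225 = 99.5, so 100 per arm. That reproduces 16.2. Exact enumeration of the named Fisher test at 100 per arm gives 76.2% power, which is the baseline for costing the fix.

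**Effect of the exclusion with no true difference.** Let X (placebo) and Y (250 mg) be independent Binomial(110, 0.10). Remove a non-responders from placebo and b from 250 mg, so the test compares X/(110−a) with Y/(110−b). Sum the probabilities of all pairs with two-sided Fisher p < 0.05, and separately of those favouring 250 mg. On average 11 respond per arm, so the apparent 250 mg rate is 11/(110−b).

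| Removed from placebo | Removed from 250 mg | Apparent rates, placebo vs 250 mg | Favours 250 mg | Either direction |
|---|---|---|---|---|
| 0 | 0 | 10.0% vs 10.0% | 1.5% | 3.0% |
| 10 | 10 | 11.0% vs 11.0% | 1.5% | 3.1% |
| 5 | 10 | 10.5% vs 11.0% | 2.6% | 4.0% |
| 0 | 5 | 10.0% vs 10.5% | 2.6% | 4.0% |
| 0 | 10 | 10.0% vs 11.0% | 3.4% | 4.4% |
| 0 | 20 | 10.0% vs 12.2% | 5.9% | 6.4% |

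The nominal error in one direction is 2.5%. Balanced removals leave the error essentially unchanged. A net imbalance of 5 brings the 250 mg direction to about nominal, 10 takes it above, and 20 roughly doubles it. The total two-sided error stays below 5% until the imbalance exceeds 10, because Fisher's test is conservative at these rates. Twenty violations in one arm would be two-thirds of the 30-patient allowance, which also covers cancellations and ineligibility in all three arms.

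**Cost of keeping everyone.** Suppose 10 and 25 responders per 100 evaluable are joined by 10 non-responders per arm. The rates become 10/110 = 9.1% and 25/110 = 22.7%, and exact Fisher power at 110 per arm is 75.1%, against 76.2% for the planned 100. If 10% and 25% hold in all 110, it is 80.4%. Ineligible and never-treated patients would still be outside the set, so 110 is the upper limit.

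**The case against.** A reader might infer that patients who cannot tolerate 250 mg will be removed and that dose made to look better. The documents do not support that. Section 8.0 permits stopping for toxicity, so a patient who stops for that reason is following the protocol and is not on its face a major violation. The step from dose-related headache to violation is inference. What stands is narrower: the wording in 13.0 does not rule out classing such a patient, or one who doses erratically without formally stopping, as a violator.

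Nor do the documents say that removed patients are mostly non-responders. Section 7.2.1 gives accidental overdose as an example of medication error, so a violation need not be under-dosing, and removing responders would push the bias the other way. The larger figures also rest on one-sided removal; the evenly split case shows no material effect.

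There are real mitigations. Section 6.5 blinds patients and treating staff, which limits deliberate selection, though not imbalance driven by toxicity itself. Section 2.1 calls the aim preliminary efficacy, and 16.1 accepts leaning towards carrying a dose forward. Section 16.4.5 compares adverse events across arms, so poor tolerability would remain visible. None of these supplies an unbiased primary comparison.

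Finally, the off-study rule in 13.0 is a more direct route to losing intolerant patients than the violation rule. Without a week 8 score they can fall out under the complete-case option in 16.8. This is a fair point, and it means that deleting the violation condition alone would not be enough.

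**Conclusion.** The point holds as a weakness in the definition of the primary analysis set: an undefined post-randomisation exclusion, tied to treatment in cycle 1, with no all-treated analysis beside it. It can bias either dose-versus-placebo comparison. Neither the direction nor the size can be fixed from the documents, and it would go too far to say that the rule will favour 250 mg.

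If removed patients are non-responders and there is no true effect, the distortion is nil for balanced removals, modest for a net imbalance of up to about 10 patients, and material at 20, which is an extreme case. These results rest on 110 randomised per arm and a 10% response in both arms. The change is worth making because it is cheap and removes the dependence on how violations happen to fall.

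**What to change.** In 16.3, define the primary set as all randomised eligible patients who took at least one dose, analysed in the assigned arm whatever their cycle 1 dosing, and delete the major-violation condition. State that a patient without a valid week 8 BFI usual-fatigue score counts as a non-responder in the primary analysis, with the 16.8 imputations as sensitivity analyses. Without that rule, restored patients who went off study could drop out again.

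Keep the current evaluable set as a labelled sensitivity analysis, and report major violations by arm with reasons.

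The cost is wording in 13.0 and 16.3 and one additional analysis, within the planned 330 patients. Estimated response rates may be slightly lower because poor adherers and patients without a score stay in the denominator. Under the dilution assumed above, that costs about one percentage point of exact power.
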